Step 1: A HIPAA Waiver will be used to access MHS Genesis to obtain all joint surgeons' case lists for those patients scheduled for surgery, all those not scheduled for a TKA will be removed from the list. The principal investigator will review case lists to identify name, TKA procedure, date scheduled for TKA, and phone. Patients scheduled for a TKA will be contacted within two weeks of their surgery to discuss the study. Study inclusion and exclusion criteria will be reviewed with patients who are interested in participation to ensure they are eligible. Those who are eligible will be scheduled for an appointment with the principal investigator before TKA surgery, ideally at their pre-op visit (standard of care visit) but may occur on the day of their surgery, to review consent documents and answer any questions. In order to ensure patient understanding, a copy of the consent documents will be emailed (if email address is provided) to the patient prior to the appointment to allow him/her to review the consent in advance.

Step 2: Patients return for their appointment to review and sign the consent documents either at their pre-operative visit or day of surgery. Consents will be signed either during their pre-operative appointment in a clinic exam room or during the day of their surgery in the PACU. Consenting a patient in the PACU on the day of surgery is a last resort and all efforts will be made to complete consents during pre-operative clinic visit. During the consent phase the PI and/or AI will not be in military uniform and will not have their rank displayed. After consent documents are signed, participants are assigned to a study group. Due to academic time constraints (i.e. deadlines to complete and present the research), an alternating convenience sample approach will be taken for study group assignment. Each participant will be assigned a subject ID number based on their order of enrollment (e.g., the first participant enrolled will be assigned 1, second participant enrolled assigned 2, and so on). Every participant with an odd number will be placed in the trigger point injection group (experimental) and those assigned an even number will be placed in the sham injection group (control). Those in the trigger point injection group will have an E after the number and

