those in the sham injection group an S. The study participants will not know which study group they will be assigned to. An equal number of participants will be included in each group (ie, trigger point injection vs. sham injection).

Step 3a: (Trigger point injection group) The principal investigator will identify relevant structures to include the vastus medialis, vastus lateralis, medial, and lateral gastrocnemius muscle bellies by utilizing anatomical landmarks. Once those structures are identified, each area will be prepped in an aseptic fashion with alcohol swabs. Two injections will be made in each muscle belly. Each injection will include 0.5 mL of 1% lidocaine without epinephrine. A total of eight injections will be administered with a total of 4 mLs of 1% lidocaine without epinephrine using a 1 ½" 25-gauge needle. A separate needle and syringe will be utilized for each of the four muscle bellies. Careful consideration to avoid neurovascular structures will be taken by retracting the plunger to ensure needle placement is outside vascular structures with each injection. A blind will be placed between the patient and the needle in order for the patient not to witness the injection, which is the same protocol as the sham injection. The blind used will be a drape or other soft item held by a person not involved with the study to obscure the vision of the subject during the injection and allow the investigator to use both hands to safely conduct the injection and aspiration procedure. The local anesthetic will be massaged into the area to ensure the medication disperses thoroughly into the muscle belly. After the needle is removed, the area will be cleaned with alcohol swabs and a bandage will be applied. This will be completed on POD 0 (ie, the day of the TKA procedure). Within the informed consent the consenting verbiage will ensure that the participants will not be able to identify injection technique that will identify whether they are in the sham or experimental group.

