11.0 Statistical/Data Analysis Plan

11.1 Data Analysis Plan and Statistical Considerations:

List the statistical methods to be used to address the primary and secondary objectives, specific aims, and/or research hypotheses. Explain how missing data and outliers will be handled in the analysis. The analysis plan should be consistent with the study objectives. Include any subgroup analyses (e.g., gender or age group). Specify statistical methods and variables for each analysis. Describe how confounding variables will be controlled in the data analysis.

Demographic (age at time of surgery, BMI, sex, active duty/dependent/retiree status), medical (ICD code, nicotine use, history of diabetes, prior pain medications), laterality of the TKA (left or right), discharge disposition, and anesthetic block type (spinal, adductor, or femoral nerve block) data will be summarized overall and as a function of injection group using descriptive statistics (eg, mean, standard deviation, median, minimum, maximum, frequency, percentages) and 95% confidence intervals to describe the sample. Appropriate inferential statistics (eg, independent samples t tests, chi square tests) will be performed to determine if there are statistically significant differences in any of these variables between the two injection groups. If so, multivariable techniques (eg, ANOVA or regression) including these potentially confounding variables in the analyses and/or stratification will be undertaken.

VAS pain scores and the dosage (MME) of opioids will be evaluated in patients as a function of injection type (ie, trigger point injection vs. sham injection) at each time point. Data will be assessed for normality and homogeneity of variance to determine whether parametric (eg, independent samples t tests, repeated measures ANOVAs) or nonparametric (eg, Wilcoxon Mann Whitney tests, Skillings-Mack tests) methods are appropriate.

In addition, the number of patients with a VAS>40 (indicating a “significant” level of pain) will be calculated and compared in each group and at each time point using the chi-square test (or the Fisher’s Exact test if assumption regarding minimum expected cell counts is not met) as well as McNemar’s tests.

The critical alpha level will be set at .05. Missing data will be handled using the “pairwise deletion” method; this method still includes patients with some missing data in the analyses when possible.

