Patients will be recruited through use of a HIPAA Waiver to access joint surgeon case lists. Patients scheduled for a TKA will be contacted by the principal investigator and informed of the study. Those who desire to participate will have study inclusion/exclusion criteria reviewed to determine eligibility. Those eligible will be scheduled a consent appointment. The investigator will offer to email (or provide by hard copy) consent document to review prior to the appointment. When patients return for consenting, they will be taken to a private room (clinic exam room or private room in the PACU) to conduct the consent procedures. Consent documents will be reviewed with patients and any questions asked will be answered. Patients who desire to enroll in the study will sign the consent documents. The investigator will sign the consent documents, then provide a copy to the patient. During the recruitment and consenting phase, the PI or AI will not be in military uniform or have their rank visible.

13.5 DoDI 3216.02 requires an ombudsman to be present during recruitment briefings when research involves greater than minimal risk and recruitment of Service members occurs in a group setting. If applicable, you may nominate an individual to serve as the ombudsman.

N/A
 Propose ombudsman

13.6 Withdrawal from Study Participation:

Explain the process for withdrawal and specify whether or not the subjects will be given the opportunity to withdraw their data or specimens in the event they wish to withdraw from the study

At any point in the study participants can self-withdrawal from the study if they have a poor response to the injections, are unable to tolerate all injections, not willing to complete questionnaires, intraoperative complications (pulmonary embolism, deep vein thrombosis, surgical site infection, multiple or other), not willing to bring in their medications or if they choose to no longer participate in the study. However, any data collected prior to withdrawal will still be analyzed.

14.0

Risks and Benefits

14.1

Risks of Harm:

Identify all research-related risks of harm to which the subject will be exposed for each research procedure or intervention as a result of participation in this study. Consider the risks of breach of confidentiality, psychological, legal, social, and economic risks as well as physical risks. Do not describe risks from standard care procedures; only describe risks from procedures done for research purposes

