The potential benefits of this study include a decrease in pain levels following TKA. This could result in decreased risk for opioid use disorder. Also, this may secondarily improve recovery and allow for easier participation in physical therapy.

14.5

Privacy for Subjects:

Describe the measures to protect subject's privacy during recruitment, the consent process, and all research activities, etc.

All consents and other information will be stored on a CAC enable computer that is password protected only accessible to investigators. All consents will be performed by either the PI and/or AI without official military uniforms or ranks displayed in a private exam or PACU room. Hard copy consent documents will be stored in a locked drawer, separate from other study documents, and saved for at least six years after study closure. After this period, the hard copy, and electronic study documents will be destroyed by shredding and/or files deleted.

14.6

Incidental or Unexpected Findings:

Describe the plan to address incidental findings and unexpected findings about individuals from screening to the end of the subject's participation in the research. In cases where the subject could possibly benefit medically or otherwise from the information, state whether or not the results of screening, research participation, research tests, etc., will be shared with subjects or their primary care provider. State whether the researcher is obligated or mandated to report results to appropriate military or civilian authorities and explain the potential impact on the subject

If any incidental unexpected findings are identified by the investigators during the medical record review (i.e., capturing medical or surgical history data), he/she will inform the participant and his/her primary care provider to facilitate follow-up.

15.0

Study Monitoring

15.1 Your study requires either Data and Safety Monitoring Plan (DSMP) or a Data and Safety Monitoring

Board (DSMB).

- DSMP
- DSMB
- Both
- Not Applicable

16.0**Reportable Events**

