17.1 Does the study involve the use of any unique non-medical devices/equipment?

Yes No

18.0**FDA-Regulated Products****18.1 Will any drugs, dietary supplements, biologics, or devices be utilized in this study?**

- Drugs
- Dietary Supplements
- Biologics
- Devices
- N/A

18.2 Drugs, Dietary Supplements and Biologics/Vaccines details:

- Are drug(s) in this research being used in accordance to the approved labeling?
- Are drug(s) in this research being used in a manner other than its approved labeling?

Enter Dietary Supplements and Biologics/Vaccines in the Drug Information table. Complete all relevant fields in the table ("Protocol Drug Details" screen). If the question is not relevant, leave the question blank and/or do not change the default selection.

View Details	Drug Name	FDA Approved	A new drug or a new use of an already approved drug:	IND Number
⊖	Trade Drug Name: lidocaine 1-2% with or without epinephrine Generic Drug Name: Investigational Drug Name:	Yes	No	

Trade Drug Name:	lidocaine 1-2% with or without epinephrine
Generic Drug Name:	
Investigational Drug Name:	
Identify the name of the manufacturer or source of investigational drug/biologic:	Hospira
Is the drug supplied at no cost?	Yes
Is the Drug FDA Approved:	Yes
Is this a new drug or a new use of an already approved drug	No
Is an IND necessary	No
IND Number	
Who holds the IND:	N/A
IND details:	
If FDA Approved and an IND is	

not required, Please provide a rationale for exemption:	
Are you currently using this IND in another research project?	No
If yes, list the IRB Number(s):	
Dose Range:	4mL
Frequency:	once
Route of administration:	intramuscular
Will the investigational pharmacy be dispensing?	Yes
If the source is not a FDA licensed facility, provide details regarding the purity, quality, stability and sterility of the investigational drug/biologic:	
Identify who will be preparing the investigational drug /biologic for administration and describe in detail how it will be prepared:	The PI will remove the lidocaine 1% without epinephrine from the pyxis within the orthopedics clinic. Once the medical is removed the PI will wear gloves and prepare 4 25-gauge needles and 4 5 mL syringes. Once all needles are attached to the syringes the cover to the lidocaine will be removed and cleaned with alcohol swabs before each draw. Once 1 mL of lidocaine 1% without epinephrine is prepared in each syringe the needles will be recapped and immediately go to the patient's room for injection.

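### Arms alternate by odd/even enrolment number with no random sequence or concealment, so the investigators who recruit, consent and inject can know the next arm before consent is signed

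*Combined protocol and SAP*

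**What the plan says.** Section 10.1, Step 2 states that "an alternating convenience sample approach will be taken for study group assignment" and gives academic deadlines as the reason. The subject ID is the enrolment order. The rule is "Every participant with an odd number will be placed in the trigger point injection group (experimental"), with even numbers going to sham. The arm is also written into the ID: "Those in the trigger point injection group will have an E after the number and" sham participants carry an S. On arm sizes: "An equal number of participants will be included in each group". Assignment formally follows signature of the consent form.

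The roles overlap:
- **Contact:** Section 13.4 says "Patients scheduled for a TKA will be contacted by the principal investigator and informed of the study".
- **Consent:** Section 14.5 says "All consents will be performed by either the PI and/or AI without official military uniforms or ranks displayed".
- **Procedure:** Section 10.1, Steps 3a and 3b, name the principal investigator in both arms.
- **Preparation:** Section 18.2 says "The PI will remove the lidocaine 1% without epinephrine from the pyxis within the orthopedics clinic".

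The only masking described is of participants, who are not told their group and whose view is blocked by a drape. On confounding, Section 11.1 tests listed baseline variables between the groups and adds: "If so, multivariable techniques (eg, ANOVA or regression) including these potentially confounding variables in the analyses and/or stratification will be undertaken". Section 9.4 calls the study prospective and interventional and does not call it randomised.

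**The concern.** Every planned between-arm comparison of VAS and MME assumes that the arms are alike at entry apart from the injection. Under alternation, whoever knows the last arm knows the next one with certainty. Here that person also decides how the study is presented and whether consent goes ahead. At the earlier call and booking stage the next arm is not certain, but it can be influenced by whom the team calls and when it books. No bad faith is needed: a warmer invitation to one patient or a later booking for another is enough.

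Any resulting difference in prognosis would be read as an effect of the injection. It cannot be measured afterwards, because no pre-operative VAS is collected, and it cannot be undone once patients are enrolled. Sections 11.5 and its continuation also intend the data for future sample-size calculations and meta-analyses, so a bias would carry forward.

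**Working it through.** **1. The plan's own sample size.** Section 11.5 uses the Wilcoxon Mann Whitney test, two-sided alpha 0.05, power 0.80, and effect sizes of 1.1 (15 per group) and 1.4 (10 per group). With noncentral t power and relative efficiency 3/π, power is 0.810 at n = 15, d = 1.1 and 0.822 at n = 10, d = 1.4. Both sizes reproduce. The concern does not change the required N.

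**2. How predictable is the next arm?** A team that knows past arms and guesses the lagging arm is right in these shares of assignments:
- alternation: 100%
- mixed blocks of 2 and 4: about 72%
- fixed blocks of 4: 70.8%
- fixed blocks of 6: 68.3%
- undisclosed mix of 6, 8 and 10: about 66%
- simple randomisation: 50%

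**3. What selection could do (illustration).** SD 25 comes from Section 11.5. The rest is assumed, since the documents give no figure: no true effect; a prognostic factor correlated r = 0.3 or 0.5 with VAS; the least favourable fraction q = 0.1 or 0.2 not enrolled into active slots, and the most favourable q not enrolled into sham slots.

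Bias = 2 × 25 × r × φ(z) / (1 − q), where z is the upper-q normal quantile.
- q = 0.1: φ(1.282)/0.9 = 0.195, so bias = 50 × 0.3 × 0.195 = 2.92, or 4.87 with r = 0.5.
- q = 0.2: φ(0.842)/0.8 = 0.350, so bias = 50 × 0.3 × 0.350 = 5.25, or 8.75 with r = 0.5.

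Against the planned 28 units this is 2.92/28 = 10% up to 8.75/28 = 31%.

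Type I error of the t test (nominal 0.05; 20,000 simulated trials per setting):

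| Per arm | q=0.1, r=0.3 | q=0.1, r=0.5 | q=0.2, r=0.3 | q=0.2, r=0.5 |
|---|---|---|---|---|
| 10 | 0.058 | 0.071 | 0.074 | 0.119 |
| 15 | 0.059 | 0.083 | 0.085 | 0.164 |
| 50 | 0.092 | 0.170 | 0.182 | 0.450 |

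The Wilcoxon Mann Whitney test gives 0.055–0.150 at 15 per arm and 0.085–0.422 at 50.

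**4. Milder case.** If selection acts on active slots only, the bias halves to 1.5–4.4 units. Type I error is then about 5.1–6.7% at 10 per arm, 5–8% at 15 and 6–15% at 50.

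**5. Would the Section 11.1 trigger catch it?** Under the two-sided selection of step 3, suppose the exact selection factor were measured. A baseline t test at 0.05 would flag it in 14% (q = 0.1) to 48% (q = 0.2) of trials at 10 per arm, and in 21% to 69% at 15. A measured covariate correlated 0.5 with that factor would be flagged in 7–12% and 9–16%.

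**The case against.** The strongest reply is that alternation is openly disclosed, a reason is given, randomisation is not claimed, and the aim is exploratory. That makes it a design weakness and not a contradiction, but neither disclosure nor an exploratory label removes the bias.

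Three further points limit the claim:
- **Foreknowledge is inferred.** No section says who issues the ID or keeps the log. The associate investigator is named for consent and prescribing but never for injecting, and Section 14.2 says only that a trained provider injects. For the principal investigator, who is named in both procedure steps, the inference is strong. An associate who only takes consent would learn the next arm through the shared sequence.
- **The routes to selection are narrowed.** Case-list review extracts only name, procedure, date and phone; clinical data are abstracted after surgery; eligibility is a fixed list. This limits selection at the call but leaves the consent meeting open. Assigning after signature conceals nothing when the next number already fixes the arm.
- **The magnitudes are assumed.** The 45% figure combines the strongest selection with the ceiling of 50 per group. At the planned 10–15 per group, mild selection inflates the error only slightly.

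The objection on cost is also fair: simple randomisation can leave unequal arms. The fix takes this into account.

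**Conclusion.** The concern holds. The arm is determined by enrolment order, nothing conceals it, and the principal investigator's roles make the next assignment foreseeable at consent. Under the assumed selection strengths the bias ranges from about 1.5 units (active slots only) to 8.7 units (both arms). Type I error ranges from about 5% to 16% at 10–15 per arm and from 6% to 45% at 50. The true size is unknown and could be nil, but the design gives no means of showing that. Extending to 50 per group leaves the bias unchanged and raises the chance of a false positive. The planned adjustment covers only listed variables and is triggered by a test with little power at the planned size. This should be corrected before enrolment.

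**What to change.** Replace the odd/even rule in Section 10.1, Step 2 with a computer-generated 1:1 random list.
- **List:** use randomly varying blocks (for example 6, 8 and 10), with sizes withheld from the team and no blocks of 2. Simple randomisation is the alternative.
- **Concealment:** someone not involved in recruitment, consent or injection prepares the list and holds it, or holds sequentially numbered, opaque, sealed envelopes.
- **Timing:** reveal the arm only after consent and enrolment are recorded, immediately before the syringes are prepared.
- **ID:** keep the number as enrolment order only, without the E or S.
- **Wording:** change the promise of equal groups to about equal.

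The cost is a short amendment and one person outside the team. No patients or visits are added, and the required N stays at 30.

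Blocks are preferable because they largely avoid uneven arms. With simple randomisation of 30 patients, 96% of lists split 10/20 or closer. On the plan's own basis (Wilcoxon Mann Whitney, d = 1.1), power is 81.0% at 15/15, 79.4% at 12/18 and 76.2% at 10/20. For the t test at d = 28/25 = 1.12 it is 84% at 15/15 and 80% at 10/20. In the 20-patient fallback (d = 1.4), a 7/13 split gives 78.6% against 82.2% at 10/10, and 11.5% of simple lists of 20 are more uneven than 7/13.

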There have been limited studies aimed at the treatment of myofascial pain syndrome in the acute setting of a TKA. Mayoral et al. (2013) conducted a randomized double-blinded, placebo-controlled clinical trial where patients who underwent a TKA had dry needling completed in the pre-operative and intra-operative setting. This study demonstrated an improvement in pain scores within the first month of surgery in the dry needling group compared to a sham group. This has been the only study to date to address direct intervention for myofascial pain syndrome around the operative time frame. Henry et al. (2012) conducted a prospective study in which patients on the waitlist for a TKA were treated with trigger point injections; patients reported an improvement in pain up until the TKA procedure could be completed. Although Henry et al. did not assess pain in the post-operative setting, this study nonetheless demonstrated that myofascial pain syndrome is a component of osteoarthritis.

Despite these favorable results there are no studies that look at trigger point injections in the post-surgical setting. The aim of this study is to perform trigger point injections with administration of a local anesthetic immediately following TKA to assess the effect on pain scores. The trigger point injection/experimental group will be compared to a sham injections/control group where a superficial injection will be made into the dermis and no anesthetic will be injected. Injections will include two injections to four muscle bellies: the vastus medialis, vastus lateralis, medial, and lateral gastrocnemius muscle belly. Injections will include 0.5 mL of lidocaine without epinephrine and will be outside of the operative area distal and proximal to the joint, the popliteal fossa and incision site. With each injection the plunger will be pulled back to ensure placement of the needle is outside vascular structures. To assess the primary outcome measures, patients will complete a Visual Analogue Scale (VAS) which ranges from 0 (no pain) to 100 (severe intolerable pain) on post operative day (POD) 1 and at follow-up visits during weeks 2 and 6. The secondary outcome will assess how much opioid medication (ie, MME) was used in the immediate post-operative period through the week 6 follow-up visit.

9.3

Objectives/Specific Aims/Research Questions:

Describe the purpose and objective(s) of the study, specific aims, and/or research questions /hypotheses

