Step 3b: (Sham injection group) The principal investigator will identify relevant structures to include the vastus medialis, vastus lateralis, medial and lateral gastrocnemius muscle. Once those structures are identified using anatomical landmarks, each area will be prepped in an aseptic fashion with alcohol swabs. A needle with a syringe filled with sterile water will be inserted into the epidermis to mimic an actual trigger point injection. The needle will be left in place for 3-5 seconds to create the false perception of injection anesthetic into the muscle groups. No sterile water will be injected into the participant. Since the effects from the anesthetic block will still be active and the injections will be administered in a position that prevents the participant from viewing the procedure, participants will not know that there is nothing being injected into the area. This will occur by placing a blind between the patient and the needle in order for the participant not to see that no water will be injected. The blind used will be a drape or other soft item held by a person not involved with the study to obscure the vision of the subject during the sham injection and allow the investigator to use both hands to safely conduct the sham injection procedure. After the needle is removed the area will be cleaned with alcohol swabs and a bandage will be applied. Four separate needles and syringes will be utilized for each location. This will be completed on POD 0 (ie the day of the TKA procedure). Within the informed consent the consenting verbiage will ensure that the participants will not be able to identify injection technique that will identify whether they are in the sham or experimental group.

Step 4: On POD0 (after TKA surgery, the investigator will review MHS Genesis to obtain demographic information (age, sex, beneficiary status, BMI), morphine milligrams equivalents (MME) using the Medication Administration Record (MAR) Summary, prior pain medication history, diabetic history, tobacco use, anesthetic block type, surgical site, ICD codes, complications, and discharge disposition.

Step 5: On POD1, participants in each study group will be provided with the VAS and Opioid Use questionnaires. The VAS pain scale questionnaire will be used to report average pain scores by placing a hash mark (/) on the numbered scale

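### As written, the injected areas are massaged in the active arm but not in the sham arm: an avoidable difference between arms when the outcome is self-reported pain

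*Combined protocol and SAP*

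**What the plan says.** Section 10.1 describes the two procedures, and its Step 2 promises that participants will not know their group.

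**Step 3a (active arm).** On insertions: "Two injections will be made in each muscle belly", and "A total of eight injections will be administered". On handling of the site: "The local anesthetic will be massaged into the area to ensure the medication disperses thoroughly into the muscle belly". The area is then cleaned and bandaged.

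**Step 3b (sham arm).** The stated aim is imitation: "A needle with a syringe filled with sterile water will be inserted into the epidermis to mimic an actual trigger point injection". On the dwell: "The needle will be left in place for 3-5 seconds to create the false perception of injection anesthetic into the muscle groups". Nothing is injected. The next handling of the site is: "After the needle is removed the area will be cleaned with alcohol swabs and a bandage will be applied". The step mentions no massage and gives no number of insertions, per muscle or in total.

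**Safeguards.** Both steps place a drape so that the participant cannot see. Both say that the consent wording will keep participants from recognising the technique. For sensation, Step 3b relies on the block: "Since the effects from the anesthetic block will still be active".

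**Elsewhere.** After introducing both groups, section 9.2 says: "Injections will include two injections to four muscle bellies". The sentence names no arm, and the one after it gives a lidocaine volume. Sections 9.2 and 11.5 make the participant-completed VAS the primary outcome, measured on POD1 and at weeks 2 and 6.

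**The concern.** A sham control should reproduce everything about the active procedure except what is being tested. Step 3b takes care over this: it repeats the landmarks, the skin preparation, the drape, the cleaning and the bandage, and it adds a dwell to suggest an injection. Massage is the hands-on step that it leaves out, and an operator following Step 3b as written would not perform it.

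Two things are at stake.

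- **Blinding.** Massage is felt and not only seen. If some participants infer their arm from it, expectation can enter a self-reported pain score.
- **What is compared.** Even if every participant stays blind, massage given in one arm only is part of the contrast. A difference in VAS would then belong to injection plus massage, not to injection alone.

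**Working it through.** No formula applies to the massage question. The check is to set the two steps side by side.

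| Element | Step 3a (active) | Step 3b (sham) | Can it be matched? |
|---|---|---|---|
| Anatomical landmarks, alcohol preparation | Stated | Stated | Already matched |
| Drape | Stated | Stated | Already matched |
| Needle depth | Muscle belly | Epidermis | No, inherent in a superficial sham |
| Fluid injected | 0.5 mL per injection | None | No, inherent in this sham |
| Massage of the area | Stated | Not mentioned | Yes |
| Insertions per muscle | 2 | Not stated | Yes |
| Needles and syringes | One set per muscle (4) | Four | Already matched |
| Cleaning and bandage | Stated | Stated | Already matched |

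**Massage.** It is specified in one arm and absent from the other. Section 9.2, the only other place that could supply a procedure common to both arms, does not mention it. The difference therefore stands on any reading of the count.

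**Insertion count.** First, the plan's own figures for the active arm: 2 injections × 4 muscle bellies = 8, and 8 × 0.5 mL = 4 mL. Both agree with Step 3a. For the sham there are two readings:

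- Section 9.2 covers both arms: 2 × 4 = 8 insertions, and the gap is 8 − 8 = 0.
- The singular wording of Step 3b means one per muscle: 1 × 4 = 4 insertions, and the gap is 8 − 4 = 4.

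The four needles in Step 3b do not decide between them. The active arm also uses one needle per muscle, and makes two injections with each. The text allows a gap of 0 or 4 and fixes neither.

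**Size of bias.** A bias in VAS units would require the share of participants who infer their arm and the shift in their ratings when they do. The documents give neither, so no figure is derived here.

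**The case against.** The strongest reply is that the plan does answer touch, not only sight. Step 3b expects the block to be active during the procedure, and no passage shows that it fails at these sites. Block type varies between participants (section 10.2), but that alone does not show residual sensation. A participant would also need to know that massage marks one arm; the consent wording is meant to withhold technique, and each person undergoes only one procedure. All of this stands as a reason to think that guessing may be limited. It does not make the procedures equal: massage would still differ between arms if nobody felt anything.

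A second reply is that massage is there to disperse the drug and so belongs to the active package, and that the sham already differs in depth and volume. That is fair as a description. But depth and volume cannot be matched in a superficial sham, whereas hands-on contact can, and Step 3b sets out to imitate the procedure. Matching it would not make the sham identical; it would remove a difference that need not be there.

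A third reply is that section 9.2 already sets the sham count. It may. A reader might infer from Step 3b that the sham receives four insertions against eight. The documents do not support that as a finding, because the section 9.2 sentence follows the description of both groups and can be read as covering both.

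A reader might also infer that skin marking differs, since the marking method appears only in the lidocaine administration instructions in section 18.2. Section 14.2 says that all injection sites will be marked, so no difference is shown.

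**Conclusion.** The concern holds for massage. As written, the active arm receives massage of the injected areas and the sham arm does not. This is avoidable, and it matters because the primary outcome is self-reported. It rests on reading Step 3b as complete: if the sponsor already intends sham massage, the gap is in the text and not in the conduct.

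For the insertion count, the conclusion is only that Step 3b should be reconciled with section 9.2. The gap is 0 or 4, depending on the reading.

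A reader might go further and conclude that blinding will fail or that the VAS comparison is biased. The documents do not show either. They show that following the text permits an unmatched component; how far it would move the VAS cannot be derived from them. Sample size and planned analysis are not affected. The point is worth fixing because the change is cheap and cannot be made for participants already treated.

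**What to change.** Reconcile section 10.1 Steps 3a and 3b with section 9.2, so that Step 3b:

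- includes the same massage contact after needle removal as the active arm receives; and
- states that the number of insertions per muscle matches the active arm.

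Section 9.2 should say explicitly that its count applies to both arms. How the active injection is delivered should not change.

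The cost is a few sentences of protocol text and slightly more time per sham procedure. Only if the sham would otherwise have used one insertion per muscle does it add up to 8 − 4 = 4 superficial insertions per sham participant. These would carry minor risks of the kind that section 14.1 already lists, such as pain, bleeding and infection.
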